#### 8.3.1 Level of Significance, Multiple Comparisons and Multiplicity

There are two active treatment groups (10 mg and 20 mg) in the study. Each of the two active treatments will be compared to the control (two hypothesis tests for the primary endpoint). The comparison of each of the two treatment groups against control for the primary endpoint will be performed using the Hochberg step up procedure, where if the largest p-value is <0.05, then the null hypothesis will be rejected for both groups. If the largest p-value is >0.05, then the critical value for the second test will be at two-sided 0.025.

To control for study-wise type 1 error rate, a fixed-sequence hierarchical testing procedure will be applied to adjust for multiplicity arising from multiple secondary endpoints. The hierarchical testing order for the secondary endpoints are:

- 1. Change from baseline to Month 6 in the sum of MDS-UPDRS Part II+III (OFF-state)
- 2. Change from baseline to Month 6 in MDS-UPDRS Part III (OFF-state)
- 3. Change from baseline to Month 6 in MDS-UPDRS Total score (OFF-state)
- 4. Percentage of Responders with "Much Improved" or "Very Much Improved" on PGIC (ON-state)
- 5. Change from baseline to Month 6 on CGIS (OFF-state)

If the primary endpoint of both dose groups are statistically significant, the secondary endpoints for each dose group will be tested in a hierarchical manner at alpha 0.025. If the primary endpoint of a specific dose group is statistically significant, the secondary endpoints for that dose group will be tested in a hierarchical manner at alpha 0.025. If the primary endpoint of both dose groups are not statistically significant, the hypothesis testing for all subsequent endpoints will be considered exploratory. Two flowcharts are also presented in the following.

All other exploratory endpoints are considered supportive and no adjustment for multiplicity will be applied.

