For PGIC, responders are defined as responses with score 1 (very much improved) and score 2 (much improved). PGIC will be analyzed for responders (scores 1 and 2) using logistic regression method.

Descriptive statistics for each visit will be produced for the PGIC.

Change from baseline to Month 6 on CGIS – OFF-state

The clinical global impressions scale on the severity of movement impairment as assessed by the site rater. Site raters will be asked: Considering your total clinical experience with the Parkinson disease population, how ill is the patient's movement at this time? Answers were based on a 7-point scale, with 1= not assessed, 2= very mild, 3= mild, 4= moderate, 5= moderate severe, 6= severe, 7= extremely severe.

The assessment is done at baseline visit and during visits at the clinic (Month 1, Month 2, Month 3, and Month 6) and OFF-state i.e., 12 hours after last intake of medication of standard of care for Parkinson's disease.

For CGIS, responders are defined as a decrease in CGIS score from baseline to Month 6. CGIS will be analyzed for responders using logistic regression method.

Descriptive statistics and change from baseline for each visit will be produced for the CGIS.

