#### 8.7 Adjustment for Covariates

Baseline value will be used as a covariate in the MMRM analyses for the primary efficacy endpoint (see Section 8.3.7).

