#### 8.10.2 Clarifications Based on Food and Drug Administration (FDA)'s Feedback

The interim analysis for sample size re-estimation has been completed in March 2023. Based on the interim analysis results and sample size re-estimation decision rules, the results of the interim analysis suggested to increase the sample size to 180 randomized subjects per arm. As of June 9, 2023, the study has completed enrollment with a total sample size of 522 (174 per arm) subjects.

The original evaluable sample size was 120 per arm, and a 20% drop out rate was assumed, which rendered to a sample size of 150 randomized subjects per arm (120/0.8=150). Based on the blinded data review, we noticed a low dropout rate of approximately 6%. With this dropout rate, 180 per arm randomized subjects will lead to 170 (180\*0.94) evaluable subjects per arm, which is around 42% increase from originally calculated sample size of 120 per arm (170/120=1.42). The sample size increased was considered reasonably small (42%) based on the Metha and Pocock (2011) paper that the overall Type I error rate will not be inflated.

The sample size re-estimation for our 3-arm study was handled by the worst-case scenario rules in Table 3 below. The sample size re-estimation method evaluates the conditional power in relationship to a pre-specified decision rule defined by ranges of attainable conditional power values. Only an increase in sample size was possible under this approach if observed conditional power was within the Promising Zone.

Outcome	Worst-case Scenario Approach
Both doses Unfavorable	Study proceeds with originally planned sample size
One dose Unfavorable	Study proceeds with sample size re-estimation increase
One dose Promising	suggested by one dose comparison in Promising Zone
One dose Unfavorable	Study proceeds with originally planned cample size
One dose Favorable	Study proceeds with originally planned sample size
	Study proceeds with larger of the sample size re-
Both doses Promising	estimation increases suggested by two dose comparisons
	in Promising Zone
One dose Promising	Study proceeds with sample size re-estimation increase
One dose Favorable	suggested by one dose comparison in Promising Zone
Both doses Favorable	Study proceeds with originally planned sample size

Table 3. Worst-case Scenario Approach to Sample Size Re-estimation for Multiple Dose Comparisons

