According to Chen, Yuan and Li (2018), the bias and error rate using the original maximum likelihood estimator (MLE) point estimator and confidence interval should be small and appropriate to use in the final analysis. In addition, the interim analysis was done using the original primary endpoint MDS-UPDRS Part II+III. Based on the Agency's feedback, the original primary endpoint is changed to MDS-Page 24 of 28 UPDRS Part II, and MDS-UPDRS Part II+III is kept as a secondary endpoint. Thus, the results of interim analysis are not relevant to the new primary endpoint. With a sample size of 174 per arm, the study will have 90% power to detect a treatment difference of 3 assuming a common SD of 8, based on a 2-sided t-test with alpha of 0.025.

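### SAP 8.3.8 gives the CGIS responder logistic regression no model terms; putting the already collected baseline CGIS score in the model would usually raise its power at almost no cost

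*SAP*

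**What the plan says.** SAP 8.3.8 defines a CGIS responder as a subject whose score decreases from baseline to Month 6. The whole analysis instruction is that "CGIS will be analyzed for responders using logistic regression method". The PGIC instruction in the same section is equally short: "PGIC will be analyzed for responders (scores 1 and 2) using logistic regression method". Neither sentence names a model term, not even treatment.

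Baseline adjustment appears in two other places. SAP 8.3.3 puts the baseline value into the MMRM, which is the model for endpoints treated as continuous. SAP 8.7, the section on covariates, says: "Baseline value will be used as a covariate in the MMRM analyses for the primary efficacy endpoint". Neither reaches a logistic model.

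SAP 8.3.8 and the Schedule of Events show CGIS rated at baseline and at Months 1, 2, 3 and 6. The scale runs from 2 (very mild) to 7 (extremely severe), and code 1 means not assessed.

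CGIS is fifth and last in the fixed sequence of SAP 8.3.1. If the primary endpoint succeeds for a dose, "the secondary endpoints for that dose group will be tested in a hierarchical manner at alpha 0.025".

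**The concern.** Whether a subject can show a decrease depends on where the subject starts. If code 1 is not a severity grade, someone rated 2 at baseline has no genuine room to fall. Someone rated 4 or 5 has room, and regression to the mean also pulls that subject down. Baseline CGIS is therefore likely to explain part of the variation in response, and a treatment-only model leaves that part in the noise.

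At stake is the CGIS claim for each dose. A treatment-only test keeps its type I error but is likely to miss a real effect more often than it need. A chance difference between arms in starting CGIS also passes straight into the observed responder difference. The test's error rate already covers that, but it costs precision. Because no terms are written down, the choice of model for a formally tested endpoint also stays open.

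**Working it through.** **1. Reproduce the plan's own figures.** The documents give no power figure for CGIS. For the primary endpoint, SAP 8.10.2 says "the study will have 90% power to detect a treatment difference of 3 assuming a common SD of 8". That is for 174 per arm and a two-sided test at 0.025. Normal approximation:

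- standard error = 8 × √(2/174) = 0.858
- 3/0.858 = 3.498; 3.498 − 2.241 = 1.257; power = Φ(1.257) = 89.6% (noncentral t: 89.3%)

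The stated 90% reproduces. So does the 120 per arm of SAP 6: 2 × (5.59/2.55)² × (2.241 + 1.282)² = 119.3, rounded up to 120.

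**2. Inputs for CGIS.** From SAP 8.10.2: "the study has completed enrollment with a total sample size of 522 (174 per arm) subjects", with dropout of about 6%, so 174 × 0.94 = 163.6, about 164 per arm. Two-sided alpha is 0.025 (SAP 8.3.1). Everything else is assumed: the baseline category mix, the baseline-to-Month-6 correlation and the effect size.

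**3. Approximate formula.** If baseline category explains a share R² of the variance in response, adjustment divides the expected test statistic by √(1 − R²).

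- Unadjusted power 80%: expected statistic 2.241 + 0.842 = 3.083.
- R² = 0.10: 3.083/√0.90 = 3.250; Φ(3.250 − 2.241) = 84.3%, a gain of 4.3 points.
- R² = 0.20: 3.083/√0.80 = 3.447; Φ(1.206) = 88.6%, a gain of 8.6 points.
- R² = 0.40: 3.083/√0.60 = 3.980; Φ(1.739) = 95.9%, a gain of 15.9 points.
- R² = 0.02: a gain of 0.9 point.

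**4. Simulation with no score of 1.** Latent bivariate-normal severity was cut into categories 2 to 5. The Wald test from logistic regression on treatment alone was compared with treatment plus linear baseline CGIS. The effect was set so that unadjusted power is near 80% or near 50%. Simulation error on a gain is about 1 point; R² is from the 80% runs.

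| Baseline mix, categories 2/3/4/5 (%) | Correlation | R² | From about 80% | From about 50% |
|---|---|---|---|---|
| 10/50/35/5 | 0.60 | 0.197 | 81.5 → 90.2 (+8.7) | 48.4 → 60.2 (+11.8) |
| 10/50/35/5 | 0.75 | 0.149 | 78.2 → 84.3 (+6.1) | 46.6 → 54.3 (+7.7) |
| 10/50/35/5 | 0.90 | 0.098 | 79.8 → 84.2 (+4.4) | 47.7 → 53.4 (+5.7) |
| 20/50/25/5 | 0.60 | 0.225 | 79.8 → 89.8 (+10.0) | 50.2 → 61.5 (+11.3) |
| 20/50/25/5 | 0.75 | 0.178 | 79.7 → 87.3 (+7.6) | 50.7 → 59.0 (+8.3) |
| 20/50/25/5 | 0.90 | 0.117 | 80.5 → 85.9 (+5.4) | 46.7 → 54.4 (+7.7) |
| 5/35/45/15 | 0.60 | 0.162 | 79.6 → 86.9 (+7.3) | 49.8 → 56.4 (+6.6) |
| 5/35/45/15 | 0.75 | 0.117 | 80.5 → 85.5 (+5.0) | 49.5 → 55.0 (+5.5) |
| 5/35/45/15 | 0.90 | 0.073 | 78.6 → 83.0 (+4.4) | 48.8 → 51.6 (+2.8) |

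**5. Fixed responder rates by category, from about 80%.** The gain is 0 if response does not depend on baseline. It is 1.5 points with 10% of subjects at the floor and flat rates above it, and 4.3 with 20% at the floor and flat rates. It is 6.4 with 20% at the floor and a moderate gradient, and 11 with a steep gradient. It reaches 15.6 only with 30% at the floor and rates of 0/10/50/75% (R² about 0.45).

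**6. Effect of code 1.** As written, a numeric move from 2 to 1 would count as a decrease. With the 20/50/25/5 mix, a latent effect of 0.35 SD and an assumed lower cut, allowing a score of 1 at Month 6 reduces the gain from 10.5 to 4.3 points at correlation 0.7, and from 6.1 to 0.5 at 0.85. At 0.93 the gain is 0 to 2 points either way. Over correlations of 0.5 to 0.85 at 0.35 SD, gains are about 4 to 13 points when a score of 1 cannot occur and about 1 to 10 when it can.

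**7. Type I error.** Null simulations gave 1.8 to 2.1% against the nominal 2.5%, so adjustment causes no inflation.

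**8. Chance imbalance (assumed rates).** With 20% at the floor, the standard error of the difference in floor share is √(2 × 0.2 × 0.8/164) = 4.4 points. If floor subjects respond at 0% and the rest at 40%, a two-standard-error imbalance moves the unadjusted responder difference by 8.8 × 0.40 = 3.5 points.

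**The case against.** The strongest reply is that the SAP is silent, not wrong. A reader might infer that it rules baseline out of the logistic model. It does not: 8.3.8 lists no terms at all. Nor is 8.7 a complete list, since it names only the primary endpoint's MMRM while 8.3.3 and 8.3.8 give the secondary MMRMs the same covariate. This stands. The finding is an unspecified model with a better specification at hand.

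The size is also open to challenge. A reader might take a figure such as 4 to 15 points as a property of this trial. The documents cannot support that. The 0.35 SD effect is close to the Part II planning ratio (3/8 = 0.375), but that belongs to a different scale. The gain also depends on how code 1 is treated, so the size cannot be separated from that question. The direction survives; a single range without conditions does not.

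Two more inferences are tempting and fail.

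- **PGIC.** PGIC has no baseline rating and is itself a rating of change, and no section shows that baseline Part II predicts it. A weakly prognostic baseline severity (R² 0.003) gave a gain of 0.3 point, so no PGIC power gain can be claimed.
- **The hierarchy.** One might say that weak power at CGIS blocks later tests. Nothing follows CGIS, and it is reached for a dose only after the primary and four secondary endpoints succeed.

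Finally, SAP 8.3.1 names the endpoint as change from baseline in CGIS. If that is reconciled to an MMRM on the score, 8.3.3 already supplies the covariate and this point falls away.

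**Conclusion.** The point holds for CGIS as a modest, low-cost improvement. The responder model has no stated terms, response is defined relative to a rating that is already collected, and a treatment-only test would be valid but usually less powerful. The gain from adjustment is roughly 1 to 13 points of power. That rests on assumed category mixes, correlations of 0.5 to 0.85, a latent effect of 0.35 SD, 164 subjects per arm and two-sided 0.025. It approaches zero if response barely depends on the starting category or if baseline and Month 6 ratings are very highly correlated. Only the CGIS claim itself is affected.

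**What to change.** Before unblinding, add to SAP 8.3.8 and 8.7 that, if the CGIS responder analysis is kept, its logistic model contains treatment and baseline CGIS score. Enter the score as a linear term: with categorical coding, a floor category with no possible responders can cause separation. Report the standardised (marginal) difference in responder percentage with its confidence interval beside the odds ratio.

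The cost is a sentence or two of SAP text and one extra estimate, with no new data and no change to the responder definition. The one small downside is that the adjusted odds ratio is conditional on baseline and differs from the marginal one. The standardised difference keeps the result on the scale of responder percentages.

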#### 8.3.9 Exploratory Analysis

Exploratory endpoints in this clinical trial are

- Change from baseline to Month 6 in the plasma biomarkers measured
- Change from baseline to Month 6 in the WAIS coding test OFF-state
- Change from baseline to Month 6 in MMSE OFF-state
- PK analysis.

Changes from baseline to Month 6 in the plasma biomarkers measured

Potential biomarkers to be measured in plasma are Neurofilament Light (NFL), Glial fibrillary acidic protein (GFAP) and TDP43.

Change from baseline to Month 6 in WAIS IV coding test – OFF-state

In the digital symbol coding test individuals are asked to record associations between different symbols and numbers within time limits. The Total score is the sum of all the correctly coded numbers. The assessment is done by the investigator at baseline, Month 2, and Month 6 and OFF-state i.e., 12 hours after last intake of medication of SOC Parkinson's disease.

Descriptive statistics and change from baseline for each visit will be produced for the WAIS coding test.

Change from baseline to Month 6 in MMSE - OFF-state.

The MMSE is a 30-point test, widely used test of cognitive function. The MMSE will be assessed by the investigator at screening, baseline, and Month 6. The MMSE comprises sections on orientation to place, orientation to time, registration, attention and calculation, recall, naming, repetition, comprehension, reading, writing, and drawing. The assessment is done by the investigator at screening, at baseline and at end-of-treatment visit and OFF-state i.e., 12 hours after last intake of medication of SOC Parkinson's disease.

Descriptive statistics and change from baseline for each visit will be produced for the MMSE.

#### PK analysis

Plasma concentration-time data for buntanetap will be listed and summarized descriptively (number of subjects (N), mean, geometric mean, median, SD, coefficients of variation (CV), minimum, and maximum) for the SAF.

Plasma buntanetap PK parameters will be calculated using a non-compartmental methods. Calculations will be based on the actual sampling times recorded during the study. The following PK parameters will minimally be determined, as data permit: Area under the curve (AUC),  $C_{max}$ ,  $T_{max}$ ,  $t_{/2}$ , and CL. A separate PK SAP will include details on PK parameters derivations and statistical analyses based on the PK set.

#### 8.3.10 Exposure to Treatment

Duration of exposure will be summarized quantitatively using the number of days on study drug for each patient, displayed by treatment group. Duration will be calculated as (last dose date – first dose date + 1).

Compliance with treatment will be assessed as the percentage of tablets taken in relation to number of tablets to be taken.

Compliance with study drug (%) = 
$$\frac{Total number of tablets taken}{Number of tablets expected}$$

Exposure and compliance will be presented using summary statistics by treatment group.

#### 8.3.11 Medical History and Concomitant Medications

Medical history will be coded using the most recent version of the Medical Dictionary for Regulatory Activities (MedDRA). Additionally, a listing of the relevant medical history will be provided.

Prior and concomitant medications will be summarized by treatment group, by the number and percentage of subjects taking each medication, classified using World Health Organization (WHO) Drug Dictionary Anatomical Therapeutic Chemical (ATC) classes and preferred terms (PT).

#### 8.3.11.1 Prohibited concomitant medication

Investigational agents are prohibited 4 weeks or five half-lives, whichever is greater, prior to entry and for the duration of the trial.

Initiation of prohibited medications during the course of the study is discouraged, however, if an excluded medication is initiated after screening, the site should consult with the Project Directors and Medical Monitor for further guidance.

Buntanetap is mainly metabolized by CYP3A4 in vitro. Therefore, we recommend avoiding concomitant use of strong or moderate CYP3A4 inhibitor/inducers, examples see below according to Food and Drug Administration (FDA) guidance on drug development and drug interactions.

CYP3A4 inhibitors	Itraconazole, Ketoconazole, Azamulin, Troleandomycin, Verapamil
CYP3A4 inducers	Rifampicin

#### 8.3.11.2 Permitted concomitant medication

Per protocol concomitant treatment with anti-parkinsonian medications at stable doses for 4 weeks or greater prior to screening are allowed.

Use of the following medications is allowed only if the patients have been stable on them for at least 4 weeks before screening and will continue to be stable throughout the study:

- tricyclic antidepressants
- antipsychotics prescribed for any reason, except ≤50 mg quetiapine daily, risperidone ≤1.5 mg/day, olanzapine ≤5 mg/day, and aripiprazole ≤10 mg/day
- psychostimulants

Discontinuation and/or change of any of the above medication during the study is discouraged and should consult with the Medical Director and Sponsor for further guidance.

For any anticonvulsant medications used for epilepsy or mood stabilization, neuropathic pain indications, dosing must be stable for at least 4 weeks prior to screening.

For mood-stabilizing psychotropic agents, including but not limited to lithium dosing must be stable for at least 4 weeks prior to Screening.

The use of short acting benzodiazepines and hypnotics for treatment on an as-needed basis for insomnia or daily dosing as anxiolytics is permitted but should be avoided for 8 hours before administration of cognitive tests. For sedating medication given for any short-term use, all cognitive assessments must be administered at least 24 hours after administration of the sedative.

At this time, there is no controlled clinical data available for anyone receiving SARS-COVID19 vaccination while being treated with buntanetap. Based on the intended mechanism of action and currently available data for these vaccine candidates and for buntanetap, it is not believed that there are specific risks to consider in subjects participating in this study who have received SARS-COVID19 vaccination or who are planning to receive the vaccination. As such, SARS-COVID19 vaccination is not prohibited. If appropriate, SARS-COVID19 vaccination should be considered as a concomitant medication.

#### 8.3.11.3 Coding and imputation of incomplete dates

All concomitant medications/therapies will be classified according to ATC level 3 group text and WHO Drug Dictionary PT. The medications will be classified into categories Prior and Concomitant drug administration based on start date and end date in relation to IMP exposure.

- Prior medications are those for which end dates of the medication/therapy are strictly before date of first administration of study drug.
- Concomitant medications are those for which the period between their start dates and end dates coincide with exposure to study drug and can be further classified into:
  - Concomitant medications starting prior to first exposure to study drug having start dates strictly before first exposure to study drug and end dates on same date or after date of first administration to study drug or are ongoing.
  - Concomitant medications starting on the date of first administration of study drug or after but before or on the date of last administration of study drug

For medication and therapies with partial dates:

- If start date is completely missing, it will be assumed that the medication started before date of first administration of study drug.
- If end date is completely missing and ongoing is not ticked, it will be assumed that the medication ended before date of first administration of study drug.
- o If the only the year is available, month 6 will be imputed for the purpose of classification.
- For medications/therapies where only year and month (including imputed dates) are available this information will be used in analogy with how complete dates are used for classification, e.g.:

Start date	End date	Ongoing	IMP start date	IMP end date	Classification
2020-07	2020-07		2020-08-14	2020-09-13	Prior
2020-07		No	2020-08-14	2020-09-13	Prior
2020-07		Yes	2020-08-14	2020-09-13	CM before
2020-07	2020-08		2020-08-14	2020-09-13	CM before
2020-08	2020-08		2020-08-14	2020-09-13	CM before
2020-08		No or Yes	2020-08-14	2020-09-13	CM before
2020-08	2020-09		2020-08-14	2020-09-13	CM before
2020-09	2020-09		2020-08-14	2020-09-13	CM after
2020-09		No or Yes	2020-08-14	2020-09-13	CM after

CM: Concomitant Medication

A relative day will not be calculated for medications with incomplete dates.

The concomitant medications will be presented in a summary table broken down on timing in relation to study drug (i.e., Prior and Concomitant). Each subject will only be counted once for each medication and timing category, on a PT level in each period.

One list for each timing period will be presented for the SAF. In addition, a list of anti-parkinsonian medications will be provided.

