#### 7 Data Sets to be Analyzed

Subjects in this study must be in accordance with the criteria specified below. Subjects who do not meet all inclusion criteria, disease diagnostic criteria, or who meet any exclusion criteria may not be randomized into the study without prior approval from the Project Directors and Medical Monitor. Membership in the analysis sets will be determined in a Pre-Analysis review meeting (see Section 8.2) before unblinding.

The following analysis sets will be used for the statistical analysis and presentation of data:

- The Enrolled set (ES) will include all subjects who signed IC and meet all inclusion and exclusion criteria. All data collected from ES will be presented in listings and if relevant in tables and/or graphs. Screening failures will have selected data be presented in a separate listing if needed.
- The Intent-to-Treat set (ITT) will consist of all subjects who are randomized. The primary efficacy analyses will be based on the ITT.
- The Modified Intent-to-Treat set (mITT) will consist of all subjects who randomized, take at least 1 dose of the study drug, and have at least 1 post-baseline assessment. The mITT will be used to support the primary efficacy analyses.
- The Safety analysis set (SAF) will be the primary safety analysis set and will consist of all
  randomized subjects who receive at least 1 dose of the study drug. The safety analyses will
  be based on the SAF.
- The Per-protocol set (PPS) will consist of all mITT subjects who complete at least 145 days treatment exposure (Last dose date First dose date + 1 >= 145 days) without any major protocol deviations that potentially could impact the primary efficacy endpoint. The PPS will be used to support the primary and secondary endpoints as supportive analyses.
- The PK set will analyze all available data from safety subjects receiving buntanetap and with at least one sampling profile allowing derivation of at least one PK parameter. Intense PK

subgroup is only in the US. 16-people per group will go through 10hr sampling timepoints at 0, 1hr, 1.5hr, 2hr, 3hr, 4hr,5hr, 6hr, 7hr, 8hr, 9hr, and 10hr (±10 mins for all collection timepoints).

Protocol deviations leading to exclusions from PPS include but are not limited to the following:

- Non-fulfilment of all inclusion criteria
- Fulfilment of at least one exclusion criterion
- Use of certain concomitant medications (for details see section 8.3.11)

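### The SAP's rule for a missing medication end date has no start-date condition, so it contradicts the section's own definition of concomitant use and two cases in its example table

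*SAP*

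**What the plan says.** SAP 8.3.11.3 sorts medications into Prior and Concomitant by their dates relative to study drug. The definitions are:

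- Prior: "Prior medications are those for which end dates of the medication/therapy are strictly before date of first administration of study drug".
- Concomitant, on-treatment start: the start falls on or after the first dose and no later than the last dose. This category needs no end date.
- Concomitant, earlier start: began before first exposure and ended on or after the first dose date, or is ongoing.

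The rule for a record with no end date at all and the ongoing box left blank is: "it will be assumed that the medication ended before date of first administration of study drug". It carries no condition on the start date.

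An example table then illustrates records for which only year and month are known, with study drug given from 2020-08-14 to 2020-09-13. Three of its rows cover a blank end date with ongoing recorded as No, two of them combined with Yes:

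- "2020-07 No 2020-08-14 2020-09-13 Prior"
- "2020-08 No or Yes 2020-08-14 2020-09-13 CM before"
- "2020-09 No or Yes 2020-08-14 2020-09-13 CM after"

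The classification is used for the summary table by timing and for one list per timing period in the safety set. SAP 7 names, among the deviations that lead to exclusion from the per-protocol set, "Use of certain concomitant medications (for details see section 8.3.11").

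**The concern.** The written rule and the example table cannot both be followed. The table looks at the start month when the end date is blank and ongoing is No. The sentence ignores the start and always returns Prior. A programmer working from the sentence and one working from the table would produce different Prior and Concomitant outputs from the same records.

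The records at risk are those with a start on treatment, no end date and ongoing unticked. These are medications begun during the trial, which a concomitant-medication summary is meant to show. Under the literal sentence they would be counted as finished before treatment began. The SAP pays attention to such use elsewhere: 8.3.11.1 deals with excluded medications begun after screening, and 8.3.11.2 requires certain permitted medications to stay stable throughout the study.

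**Working it through.** **Inputs.** All come from SAP 8.3.11.3: the missing-end-date rule, the Prior and Concomitant definitions, and the nine printed example rows. Two rows give ongoing as No or Yes. Splitting each into a No case and a Yes case gives 9 + 2 = 11 cases. The first-dose month is 2020-08.

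**What No means.** The row with start 2020-07, no end date and ongoing No is classed Prior, exactly as the sentence for an unticked box requires. No is therefore the table's notation for not ticked, and the No halves of the other two rows are fair tests of the sentence.

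**Rules compared at month level.**

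- Literal: blank end date and ongoing not Yes gives Prior. Otherwise, an end month before 2020-08 gives Prior, a start in or before 2020-08 gives CM before, and a later start gives CM after.
- Limited: as literal, but a blank end date with ongoing not Yes gives Prior only if the start month is before 2020-08. Otherwise the record is classed by its start.
- Inclusive: any blank end date is treated as continuing, and the record is classed by its start.

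| Start | End | Ongoing | SAP table | Literal | Limited | Inclusive |
|---|---|---|---|---|---|---|
| 2020-07 | 2020-07 | blank | Prior | Prior | Prior | Prior |
| 2020-07 | blank | No | Prior | Prior | Prior | **CM before** |
| 2020-07 | blank | Yes | CM before | CM before | CM before | CM before |
| 2020-07 | 2020-08 | blank | CM before | CM before | CM before | CM before |
| 2020-08 | 2020-08 | blank | CM before | CM before | CM before | CM before |
| 2020-08 | blank | No | CM before | **Prior** | CM before | CM before |
| 2020-08 | blank | Yes | CM before | CM before | CM before | CM before |
| 2020-08 | 2020-09 | blank | CM before | CM before | CM before | CM before |
| 2020-09 | 2020-09 | blank | CM after | CM after | CM after | CM after |
| 2020-09 | blank | No | CM after | **Prior** | CM after | CM after |
| 2020-09 | blank | Yes | CM after | CM after | CM after | CM after |
| Agreement with the SAP table | | | | 9 of 11 | 11 of 11 | 10 of 11 |

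**The two mismatches differ in kind.**

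- Start 2020-09: the sentence places the end before 2020-08-14, so the medication ends before it starts. This is impossible.
- Start 2020-08: first dose was on the 14th, so a medication could have started and stopped earlier that month. The sentence's answer is possible, but it is not the one the table gives. The conflict is in classification only.

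**Complete start dates.** The table covers month-level dates. Take a full start date after first dose, a blank end date and ongoing unticked. The on-treatment definition makes it concomitant, while the only explicit rule for the missing end date makes it Prior. The table does not settle this case.

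**The case against.** The best defence is that the section largely corrects itself. On-treatment concomitant use is defined by start date alone, and the table applies that definition. A programmer who follows the definition and the table loses no medication that started on treatment. This stands as far as it goes, but it depends on overriding an explicit, unqualified sentence, and the table does not reach complete start dates.

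Three stronger readings are tempting and are not supported:

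- *Medications would be hidden or escape review.* A medication filed as Prior still appears in the Prior list. SAP 8.3.11.3 also plans a list of anti-parkinsonian medications with no timing limit, and SAP 8.3.4 says eCRF data will generally be listed.
- *The per-protocol set would be wrong.* SAP 7 and 8.2 assign membership at a pre-analysis review of protocol deviations before unblinding. Nothing says it is derived from the Prior or Concomitant flag. An effect is possible but not shown.
- *The row for 2020-07, blank, No is also an error.* It agrees with the sentence. Treating an earlier start that is not marked ongoing as Prior is a consistent, pre-specified convention. One may prefer a more inclusive one, but that is a choice.

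Concomitant medications are also reviewed at every visit (Protocol Appendix 1) and data corrections are requested where needed (Protocol 21.1), which should keep such records few.

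**Conclusion.** The contradiction is real and can be seen within SAP 8.3.11.3 alone. Read literally, the sentence misclassifies 2 of the 11 example cases and gives an impossible date order in one of them. That count describes the example table and is not an estimate of the share of trial records affected, which the documents do not allow one to calculate.

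The consequence is limited to the Prior and Concomitant summaries and lists, and arises only if the sentence is programmed as written. The primary MMRM in the ITT set does not use this classification, and the per-protocol set is supportive only (SAP 8.3.7). The conclusion assumes that No in the table means the ongoing box was not ticked, which the 2020-07 row bears out. This is a minor correction, worth making before programming and the pre-analysis review.

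**What to change.** Add a start-date condition to the sentence. A missing end date with ongoing not ticked is taken as ended before first dose only if the known start is before first dose or, where only the month is known, the start month is before the month of first dose. Otherwise the record is classed by its start. State that no imputed end may precede the start, and say how a record with both dates missing is classed. The condition reproduces all 11 example cases, so no table row changes. It costs one SAP sentence.

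As an option, adopt the inclusive convention: treat any unresolved end date as concomitant unless the available dates show that the medication ended before first dose. This matches SAP 8.3.2, which counts an adverse event as treatment-emergent when incomplete start dates prevent a clear assignment. It would change the 2020-07, blank, No row from Prior to CM before. The small downside is a few more records counted as concomitant.
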